#### 7.7.1 Storage

Selumetinib capsules should be stored below 30°C. A full description of the appropriate storage conditions are specified on the investigational labels. Further details regarding treatment supply, storage and labelling can be found in the Pharmacy Manual (supplied separately).

#### 7.8 Concomitant Medication

Patients are required to have been established on a HAART regimen for at least 3 months prior to study entry. Their HAART regimen should not be changed while they are on study, except after discussion with the Cls. Throughout the study, patients should avoid changes to, or the addition of all concomitant medications. A wide range of drug interactions can occur with HAART. Any proposed additional medications should be checked for potential interactions using the Liverpool HIV Drug Interaction charts: http://www.hiv-druginteractions.org/Interactions.aspx. In addition, drugs that might affect the metabolism of selumetinib (CYP1A2 or 3A4 inhibitors/inducers) should be avoided: http://medicine.iupui.edu/clinpharm/ddis/table.aspx. Pre-clinical studies predict minimal significant metabolism by CYP3A4, and that, as per protocol, HAART levels are monitored in phase I, and HIV viral loads and CD4 counts in both phase I & II. No other anti-cancer treatment (including radiotherapy) or investigational therapy is permitted whilst patients are on study therapy.

Increased monitoring may be necessary if patients are started on medications which may potentially interact with HAART or selumetinib. If changes to medications are necessary the treating physician should consider whether it is in the patient's best interest to remain on study. Any changes to medications should be reported on the Concomitant Medications Form.

#### In addition:

- Patients should avoid excessive sun exposure and use adequate sunscreen protection if sun exposure is anticipated.
- Patients should avoid grapefruit juice and St John's Wort because of the possible interaction
  with selumetinib metabolism through inhibition and induction of CYP3A4 respectively and the
  potential effects they can have on the metabolism of HAART.
- Selumetinib capsules contain vitamin E in the form of D-α-tocopheryl polyethylene glycol 1000 succinate (TPGS), a water-soluble form of vitamin E which acts as a formulation excipient. The maximum daily dose of vitamin E that a study subject may receive from selumetinib is approximately 261.6mg/day. Therefore:
  - o Patients should not take any supplemental vitamin E. High doses of vitamin E have been reported to cause bleeding and interrupt blood coagulation processes.
  - Selumetinib/placebo should be administered with caution in patients who are also receiving coumarin anticoagulant medications, e.g. warfarin. These patients should have

their International Normalised Ratio (INR) monitored/ anticoagulant assessments conducted more frequently and the dose of the anticoagulant should be adjusted accordingly,

# 7.9 Assessments

# 7.9.1 Pre-treatment Screening Assessments

Within 4 weeks prior to starting trial treatment, the following are required:

- CT scan of thorax, abdomen & pelvis
- Pregnancy test in females of child-bearing potential
- Echo/MUGA.
- Ophthalmologic exam to include slit lamp examination, measurement of visual acuity, assessment of visual fields, assessment of colour vision, and overall visual assessment.
- Tumour biopsy (archived diagnostic material is acceptable if available)

Within 2 weeks prior to starting trial treatment, the following are required:

- Medical history and examination, body weight, WHO performance status, pulse rate & blood pressure (if ≥150/95 mmHg repeat 1 hour later, if still ≥ 150/95 mmHg, the patient is ineligible).
- Document evidence of histologically confirmed KS (archived diagnostic biopsy or fresh biopsy if required), HIV positivity and HAART regimen for past 3 months.
- · Blood tests for:
  - o Full blood count including Hb, WBC, neutrophils and platelets
  - Clotting studies including INR and Prothrombin time
  - Biochemistry profile including urea, creatinine & electrolytes, liver function tests (bilirubin, ALT, AST and ALP), albumin, total protein, creatine phosphokinase, calcium and phosphate.
  - HIV-1 viral load
  - o CD4 count
- Chest X-Ray.
- ECG (to include heart rate, PR, QRS Duration, QT and QTc).

Pre-treatment, day 1, the following are required:

- Medical history and examination, including symptoms and signs, body weight, WHO
  performance status, pulse rate & blood pressure
- Full examination of oral and gingival mucosa
- Document all oral and cutaneous disease using clinical photographs including a ruler where possible (See ACTG criteria, Appendix 1)
- Blood tests for:
  - o Full blood count including Hb, WBC, neutrophils and platelets
  - Clotting studies including INR and Prothrombin time
  - Biochemistry profile including urea, creatinine & electrolytes, liver function tests (bilirubin, ALT, AST and ALP), albumin, total protein, creatine phosphokinase, calcium and phosphate.
  - o HIV-1 viral load.
  - o CD4 count.
  - Angiogenic biomarkers.
  - o Pre-treatment anti-retroviral drug levels (Phase I only).
  - o Pregnancy test in females of child-bearing age.

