# 1.2 Mitogen-activated protein kinase (MAPK) Pathways and KS

MAPK pathways are signal transduction pathways utilised by many growth factor receptors including epidermal growth factor (EGF), insulin-like growth factor-1 (IGF) and platelet-derived growth factor (PDGF), which play essential roles in cell survival, proliferation and differentiation (Adjei et al. 2008). Genetic mutations and/or over expression of these growth factors, their receptors, downstream signalling proteins, or protein kinases involved in the Ras/Raf/MEK/ERK MAPK pathway have been implicated in a variety of tumours including lung cancer, melanoma, thyroid cancer and pancreatic tumours. The MAPK Extracellular signal-regulated kinase (MEK) is also stimulated by a variety of chemokines including interleukin 6 (IL-6), IL-1β, interferon-y and vascular endothelial growth factor (VEGF) and is important in mediating immune responses. MEK has also been identified as important in viral infections including HHV-8 and human immunodeficiency virus type 1 (HIV-1) during the early infection phase and reactivation following viral latency (Yang and Gabuzda 1999; Sharma-Walia, et al. 2005; Xie, et al. 2008). In KS, the HHV-8 encoded proteins viral interleukin-6 (vIL-6) and viral G protein coupled receptor (vGPCR) upregulate the Ras/Raf/MEK/ERK pathway (Vart, et al. 2007). In KS this has been shown to stimulate expression of Angiopoeitin-2 (Ang-2), a pro-angiogenic factor (Vart, et al. 2007), which may further promote KS development. Plasma Ang-2 levels have been shown to correlate with volume of disease (Wang, et al. 2004). The MAPK pathway therefore provides an attractive therapeutic target in KS.

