# 8.2 Tissue Samples

Paired tumour biopsies will be collected pre-study (diagnostic biopsy) and at the end of Cycle 2, whenever possible. At the end of Cycle 2, half the sample will be placed in RNALater for storage at -80°C. Half will be fixed in 10% formalin and embedded in paraffin. Immunohistochemistry will be used to measure pERK, down-stream targets of ERK signalling and key substrates in the JNK, p38 MAPK and PI-3K/Akt pathways.

Immunohistochemistry will also assess the expression of angiogenic factors and activated caspase 3 with TUNEL as a marker for apoptosis. Changes in pERK and key members of other cell signalling pathways identified in the sub-study of PBMCs will be assessed by Western blot using protein lysates formed by homogenization of frozen tissue biopsy sections.

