#### 13.2.2 Phase II

Phase II will investigate the efficacy of selumetinib in combination with HAART in patients with KS. Patients recruited to the recommended phase II dose in phase I will be included in phase II.

In order to keep the trial the trial size as small as possible a Simon two-stage design will be used for patient accrual.

Phase II will accrue up to a total of 25 response evaluable patients (including those from phase I). The primary outcome measure of phase II is best objective tumour response up to the end of the 6th cycle. Objective tumour response is as defined by the ACTG criteria (refer to appendix 1 for details). Both CR and PR will count as responses for the purpose of the primary outcome.

- Response rate will be estimated with 90% confidence intervals.
- Toxicity per cycle and dose intensity will be reported.
- Number of treatment cycles completed, duration of response and progression free survival at 6 months from commencing treatment will be reported
- Percentage inhibition of pERK in tumour tissue will be calculated and correlated with tumour response. Changes to downstream proteins, apoptotic pathways and adaptive changes to other MAPK pathways will be assessed.
- Percentage changes in serum angiogenic markers will be calculated and correlated with tumour response.
- Percentage changes in HIV-viral load and CD4 count will be calculated.

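### Archived diagnostic tissue of any age may serve as the pERK baseline, and freezing is specified only for the end-of-Cycle-2 biopsy, so some tumour changes cannot be attributed to selumetinib and the Western blot comparison lacks a specified baseline

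*Protocol*

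**What the plan says.** The pharmacodynamic work in tumour rests on paired biopsies, one before treatment and one at week 6 (section 2.2.2).

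- **Source of the baseline.** Section 7.9.1 places the biopsy in the four weeks before treatment, then adds "Tumour biopsy (archived diagnostic material is acceptable if available". Section 8.2 describes the pair this way: "Paired tumour biopsies will be collected pre-study (diagnostic biopsy) and at the end of Cycle 2, whenever possible". Neither section limits the age of the block or the treatment given since it was taken.
- **Storage.** Section 8.2 states "At the end of Cycle 2, half the sample will be placed in RNALater for storage at -80°C" and "Half will be fixed in 10% formalin and embedded in paraffin". It gives no corresponding instruction for the pre-study sample.
- **Assays.** Section 8.2 measures pERK and pathway substrates by immunohistochemistry. It also plans to assess changes in pERK and other pathway members by "Western blot using protein lysates formed by homogenization of frozen tissue biopsy sections".
- **Analysis.** Sections 13.2.1 and 13.2.2 carry the same line: "Percentage inhibition of pERK in tumour tissue will be calculated and correlated with tumour response".
- **Prior treatment.** Section 4.1 requires at least three months on a HAART regimen, admits patients whose disease has progressed after chemotherapy, requires progression in the past six months, and bars anti-cancer treatment in the month before starting.

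**The concern.** Percentage inhibition is a before-and-after contrast. It measures the effect of selumetinib only if selumetinib is the main thing that changed between the two samples. A diagnostic block may have been taken before the current HAART regimen, before chemotherapy, or before the recent progression that made the patient eligible. The protocol gives a reason to care: "MEK has also been identified as important in viral infections including HHV-8 and human immunodeficiency virus type 1" (section 1.2). Section 1.1 adds that starting HAART may be enough to control early disease. A shift in tumour pERK after HAART is therefore plausible without any MEK inhibitor, although the protocol does not state that it occurs.

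Relating response to pERK inhibition in tumour is the first objective in section 8.1. The PBMC sub-study also asks whether pERK in blood cells predicts inhibition in tumour. PBMC and serum baselines are drawn before dosing on Cycle 1 Day 1 (sections 8.3.1 and 8.3.3). Tumour tissue is the only pharmacodynamic measure whose baseline may come from another treatment era.

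The storage gap is a separate matter. A change measured on frozen tissue needs a frozen sample at both times, and the protocol describes one. Analysis cannot recover an aliquot that was never stored.

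**Working it through.** The protocol gives no sample size, power or expected value for the pERK analysis, so there is no stated figure to reproduce. The check compares the passages and adds simple arithmetic.

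**1. Time between the two biopsies.** The end of Cycle 2 is 2 × 21 = 42 days, or 6 weeks, after starting.
- Fresh baseline: 0 to 4 weeks before the start plus 6 weeks gives 6 to 10 weeks.
- Block predating the required HAART period: at least 3 months plus 6 weeks, about 4.5 months, with no upper limit.
- Block predating the last anti-cancer treatment: at least 1 month plus 6 weeks, about 2.5 months, with no upper limit.

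**2. Does a fresh biopsy avoid the problem?** Yes. One taken within 4 weeks of starting falls after the last anti-cancer treatment, because none is allowed in the preceding month. It also falls on HAART already taken for roughly two months or more (3 months less 4 weeks). The problem is confined to archived baselines, and among those to blocks older than current HAART or the last anti-cancer treatment.

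**3. What a shifted baseline does.** Let I be the true inhibition on drug and k the ratio of archived pERK to true pre-dose pERK. On-treatment pERK is (1 − I) times the true pre-dose level, so

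apparent inhibition = 1 − (1 − I)/k.

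The values of k are assumptions, since the documents give no pERK measurements.

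| k | I = 0 | I = 50% |
|---|---|---|
| 0.5 | −100% | 0% |
| 0.75 | −33% | 33% |
| 1 | 0% | 50% |
| 1.5 | 33% | 67% |
| 2 | 50% | 75% |

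For example, I = 0 and k = 2 gives 1 − 1/2 = 50%. I = 50% and k = 0.5 gives 1 − 0.5/0.5 = 0%. A shifted baseline can create inhibition or hide it.

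**4. Which comparisons the stored tissue supports.**

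| Baseline | Immunohistochemistry | Western blot on frozen tissue |
|---|---|---|
| Archived only | Possible: the fixed half of the Cycle 2 sample can be compared with the block | No frozen baseline provided for |
| Fresh | Possible if part is fixed | Possible only if part is frozen; section 8.2 does not say |

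**5. Does this touch the primary endpoint?** No. The Simon rule (stop at 1 or fewer responses in 16; active at 5 or more in 25; 10% against 30%) was recomputed exactly. Type I error is 0.095 against the stated 0.10, and power is 0.903 against the stated 0.90. It uses no biopsy data.

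**The case against.** The strongest reply has four parts.

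*A timed fresh biopsy is the default listing, and archived tissue spares patients a procedure.* This stands as far as it goes. The trade-off is reasonable, and a reader who inferred that the whole pERK endpoint is confounded would go too far. The problem lies in a subset of unknown size.

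*The protocol does not say that fresh baselines are not frozen, and the Laboratory Manual may cover it.* The first half stands. A reader might infer that the Western blot change analysis has no baseline in anyone and cannot be done. The text does not support that, because it is silent on how fresh pre-study biopsies are stored. The appeal to the manual is weaker: section 8.2 does not cite it, and section 8.3 cites it for courier details. A manual could not supply a matching frozen aliquot for an archived block in any case.

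*Which pairs enter a translational correlation is usually settled in the SAP.* That is fair, and the absence of such a rule is not in itself the fault. What the protocol does fix is an undated baseline and storage at one time point, and the second cannot be repaired at analysis.

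*The output is exploratory.* It supports a secondary objective with no hypothesis test or decision rule. That limits the consequence but does not remove the bias.

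Two further inferences should be resisted. Any count of affected pairs would be a guess: the archived share is not given, not every archived block predates HAART or chemotherapy, and pairs are collected only when possible. Nor does the protocol show that patients treated after chemotherapy are the likeliest to have old blocks or that they respond differently.

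**Conclusion.** The point holds in two limited parts.

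First, because archived material of any age is accepted, the baseline may predate current HAART or chemotherapy in some patients. In those patients neither percentage inhibition of pERK nor its correlation with response could be attributed to selumetinib. This rests on the eligibility and biopsy rules as written. The size of any bias is unknown, and the 33% to 50% apparent inhibition under no drug effect (k from 1.5 to 2) only illustrates the mechanism.

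Second, section 8.2 plans a change analysis on frozen tissue while specifying frozen storage at only one of the two time points. Patients with only archived material have no frozen baseline provided for, and none is specified for fresh biopsies.

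The immunohistochemistry comparison remains feasible despite the storage gap, although its interpretation still depends on when the baseline was taken. The primary response endpoint and the Simon design are unaffected. This should be corrected, but it does not threaten the trial's main conclusion.

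**What to change.** **Section 8.2.** State that any fresh pre-treatment biopsy is divided between RNALater and formalin exactly as at the end of Cycle 2. Limit the Western blot analysis of change to pairs with a frozen baseline.

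**Sections 13.2.1 and 13.2.2.** Base the main percentage-inhibition analysis, and its correlation with response, on pairs whose baseline was taken on the current HAART regimen and after the last anti-cancer treatment. Report the remaining pairs separately, labelled as such.

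**Baseline Assessment Form (section 10.1).** Record the date of the baseline biopsy, if the form does not already ask for it, so that pairs can be classified.

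The cost is a few sentences, one date field and one RNALater tube for biopsies already being taken. No additional biopsy is requested, and fresh baselines taken in the four-week window meet the restriction automatically. The downside is fewer pairs in the main pERK analysis. The storage change can help only patients enrolled from now on, since phase I is complete; the restriction and separate reporting can be applied to all patients whose biopsy dates can be established.

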### 7.9.2 Assessments during Treatment

#### 7.9.2.1 Phase I

Phase I is now complete and the recommended phase II was determined to be 75 mg bd.

### 7.9.2.2 Phase II

The following assessments will be performed every 3 weeks (+/- 1 day), on day 1 of every cycle:

- Physical examination & weight
- Pulse rate & BP.
- Adverse events using CTCAE version 4.0 criteria (see Appendix 4).
- Blood tests for:
  - o Full blood count
  - Biochemistry including urea, creatinine & electrolytes, liver function tests (bilirubin, ALT, AST and ALP), albumin, total protein, creatine phosphokinase, calcium and phosphate.

### **Blood Samples:**

- Angiogenic biomarkers on Cycle 1 Day 1 Pre-treatment, Cycle 1 Day 22/Cycle 2 Day 1, Cycle 2 Day 22/Cycle 3 Day 1, Cycle 4 Day 22/Cycle 5 Day 1 and Cycle 6 Day 22 (all +/- 1 day except Cycle 1 Day 1 Pre-treatment).
- HIV-1 viral load on Cycle 1 Day 1 Pre-treatment, Cycle 1 Day 22/Cycle 2 Day 1, Cycle 2 Day 22/Cycle 3 Day 1, Cycle 4 Day 22/Cycle 5 Day 1 and Cycle 6 Day 22, then at the end of every 3 cycles in patients continuing on selumetinib beyond 6 cycles (all +/- 1 day except Cycle 1 Day 1 Pre-treatment).
- CD4 count on Cycle 1 Day 1 Pre-treatment, Cycle 3 Day 22/Cycle 4 Day 1 and Cycle 6 Day 22, then at the end of every 3 cycles in patients continuing on selumetinib beyond 6 cycles (all +/- 1 day except Cycle 1 Day 1 Pre-treatment).
- PBMC sub-study on Cycle 1 Day 1 Pre-treatment Cycle 3 Day 22/Cycle 4 Day1 and Cycle 6
  Day 22 (participating centres only, all +/- 1 day except Cycle 1 Day 1 Pre-treatment).

Further details can be found in the Laboratory Manual.

# Additional Assessments:

- Tumour biopsy End of Cycle 2 (+/- 1 day).
- Disease evaluation on Cycle 2 Day 22/Cycle 3 Day 1, Cycle 4 Day 22/Cycle 5 Day 1 and Cycle 6 Day 22 then at the end of every 2 cycles (all +/- 1 day) in patients continuing selumetinib using ACTG criteria (see Appendix 1), with clinical photographs.
- Echocardiogram or multi gated acquisition (MUGA) scan (measurement of LVEF) to be performed on Cycles 2 Day 22/Cycle 3 Day 1 and Cycle 4 Day 22/Cycle 5 Day 1 (both +/- 1 day). If a decrease of LVEF of >10% is observed, an additional assessment may be performed at the 30 Day Post-Discontinuation Visit (+/- 3 days) and every 6 weeks thereafter (+/- 7 days) whilst LVEF continues to remain >10% from baseline. Decreases in LVEF from baseline may be investigated according to the algorithm (Appendix 7).
- All new dyspnoea AEs or worsening of pre-existing dyspnoea AEs should be followed according to the dyspnoea algorithm (Appendix 8).
- Ophthalmologic exam to include slit lamp examination, measurement of visual acuity, assessment of visual fields, assessment of colour vision, and overall visual assessment – to be performed in patients experiencing visual disturbances whilst in the trial as clinically indicated (Appendix 9).
- CT imaging of assessable disease (where present) at the end of every 2 cycles (+/- 1 day).

# 7.9.3 Off Study assessments

The following assessments will be conducted in all patients upon discontinuing selumetinib treatment:

 Patients who have a drop in LVEF>10% from baseline (measured at screening) during the course of selumetinib treatment should have an echocardiogram or MUGA scan performed after permanent discontinuation of selumetinib.

 Patients will have blood tests for full blood count, biochemistry including urea, creatinine & electrolytes, liver function tests (bilirubin, ALT, AST and ALP), albumin, total protein, creatine phosphokinase, calcium and phosphate.

# 7.9.4 30 Day Post-Discontinuation assessments

The following assessments will be conducted in all patients 30 days (+/- 3 days) after discontinuing selumetinib treatment:

- Patients who have a drop in LVEF>10% from baseline (measured during screening) during the
  course of selumetinib treatment which persists at the time of discontinuation of selumetinib
  should have an echocardiogram or MUGA performed to document reversibility (Appendix 71).
- Patients who have clinically significant full blood count or biochemistry laboratory value AEs in the off study assessments should have a further full blood count and biochemistry profile performed.
- AE and Concomitant Medication assessment (end of reporting period).

# 7.9.5 Ad Hoc Follow-Up assessments

- Patients who have experienced a drop in LVEF>10% from baseline (measured during screening) during the course of selumetinib treatment which persists at the 30 Day Post-Discontinuation visit should have repeat echocardiograms/MUGAs at 6 weekly intervals (+/- 7 days) whilst LVEF continues to remain >10% from baseline (Appendix 7).
- Patients who have clinically significant full blood count or biochemistry laboratory value AEs in the off study assessments which persist at the 30 Day Post-Discontinuation visit should have repeat further full blood count and biochemistry profiles performed at 3 weekly intervals whilst these parameters remain above ULN or baseline values.
- Patients experiencing unresolved AEs at the 30 Day Post-Discontinuation visit should have these followed up every 3 weeks until resolved.

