# **Phase II Assessments Continued**

Concomitant Medications

	Screening		Pre- treatment Day 1	Cycle 1 Day 22/Cycle 2 Day 1 (+/- 1 day)	Cycle 2 Day 22/Cycle 3 Day 1 (+/- 1 day)	Cycle 3 Day 22/Cycle 4 Day 1 (+/- 1 day)	Cycle 4 Day 22/Cycle 5 Day 1 (+/- 1 day)	Cycle 5 Day 22/Cycle 6 Day 1 (+/- 1 day)	Cycle 6 Day 22 (+/- 1 day)	Patients continuing Selumetinib (every 3 weeks, +/- 1 day)	Off Study	30-days post discontinuation Selumetinib (+/- 3 days)	Post treatment (every 12 weeks, +/- 7 days)
	Within 4 weeks	Within 2 weeks											
Other Investigations													
HIV-1 viral load		Х	Х	Х	Х		Х		Х	X (end of every 3 cycles)			
CD4 count		Х	Х			Х			х	X (end of every 3 cycles)			
Angiogenic serum biomarkers			Х	Х	X		х		x				
Tumour biopsy	Х				Х								
††PBMC Sub- study			х			x			х	X (end of every 3 cycles)			
Adverse Events													
Toxicity reporting	Monitor throughout the course of the study  Monitor throughout the course of the study												

PK – Pharmacokinetics; PBMC – Peripheral Blood Mononuclear Cell. \$ required in patients who have a drop in LVEF > 10% from baseline; # subsequent assessments to be performed in patients experiencing visual disturbances as clinically indicated;\* patients with AST, ALT or bilirubin value above ULN or baseline values at the time of the last dose of selumetinib; † required if visceral or extensive nodal disease identified on baseline CT; †† participating centres only.

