### 10 DATA HANDLING AND RECORD KEEPING

# 10.1 Data Collection

The Case Report Form (CRF) will comprise of the following forms:

Standard Forms	Summary of data recorded	Schedule for submission
Eligibility Form.	Confirmation of eligibility and satisfactory	Within 2 weeks of
	staging investigations where necessary.	registration.
Registration Form.	Patient details and Registration Number.	Within 2 weeks of
		registration.
Baseline Assessment	Details of baseline assessments inc. physical	Within 2 weeks of
Form.	exam, clinical photography, blood pressure,	registration.
	ECG, baseline LVEF, ophthalmological	
	assessment, haematology and biochemistry,	
	tumour biopsy, HIV-1 viral load, CD4 count,	
	PBMC collection (for sub study). HAART	
	regimen.	
Treatment Cycle	Details of 21-day cycle inc. physical exam,	End of every cycle. Within
Forms (separate	clinical photography, blood pressure, ECG,	1 week.
forms for cycles 1-6).	haematology and biochemistry, toxicities.	
Adverse Events	List of all adverse events.	End of every cycle. Within
Form.		2 weeks
Concomitant	List of concomitant medication.	End of every cycle. Within
Medications Form.		2 weeks.
Treatment	Details of additional treatment cycles post	End of every additional
Continuation Forms	completion of 6 cycles.	cycle. Within 1 week.
Off Study Form	Details of haematology and biochemistry	Within 2 weeks.
	assessments, potential ECHO, tumour	
	response and no. of completed cycles	
30-Day Post	Details of potential biochemistry and	Within 2 weeks.
Discontinuation	ECHO/MUGA assessments, plus follow up of	
Follow-Up Form	Adverse Events and Concomitant	
	Medications.	
12-Weekly Follow-up	Details of physical exam and clinical	Annually following
Form.	photography (every 12 weeks for 12 months	completion of treatment.
	post end of treatment).	
Ad Hoc Forms		

Additional ECHO/MUGA Scan	Details of ECHO or MUGA (to be performed in patients with symptoms (AEs) suggestive of cardiac impairment).	Within 2 weeks.
Additional Ophthalmologic Exam	Details of ophthalmologic exam (to be performed in patients experiencing visual disturbances)	Within 2 weeks.
Additional Haematology/ Clinical Chemistry Assessments	Haematology and biochemistry assessments performed until all AEs are resolved to baseline upon completion of treatment	Within 2 weeks.
Serious Adverse Event Form.	Details of SAEs	Immediately (within 24 hours) upon notification of an SAE.

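### Post-treatment laboratory and LVEF follow-up has different triggers and scope in the text and in the assessment table, and the laboratory stop rule is worded only for high values

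*Protocol*

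**What the plan says.** **Day-30 laboratory tests.** Protocol 7.9.4 applies to "Patients who have clinically significant full blood count or biochemistry laboratory value AEs in the off study assessments" and asks for both a full blood count and a biochemistry profile. In the 7.9.7 table, the day-30 column carries a mark on the liver function row only. The rows for full blood count, urea and electrolytes, and calcium and phosphate are filled at the off-study visit and empty at day 30. The footnote to the liver mark limits it to "patients with AST, ALT or bilirubin value above ULN or baseline values at the time of the last dose of selumetinib".

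**Day-30 LVEF.** All passages start from a drop of more than 10% from baseline.
- 7.9.2.2 says "an additional assessment may be performed at the 30 Day Post-Discontinuation Visit". The same optional wording covers the six-weekly scans after that, which 7.9.5 says should be done.
- 7.9.4 says the scan should be done, but only for a drop "which persists at the time of discontinuation of selumetinib".
- The 7.9.7 footnote says the scan is "required in patients who have a drop in LVEF > 10% from baseline", with no persistence condition.

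**Stop rule.** Under 7.9.5, laboratory events that are still present at day 30 lead to blood counts and biochemistry every 3 weeks "whilst these parameters remain above ULN or baseline values". The next bullet of 7.9.5 follows any unresolved adverse event every 3 weeks until it resolves, and names no test. The case report form table in 10.1 describes the additional laboratory form as "Haematology and biochemistry assessments performed until all AEs are resolved to baseline upon completion of treatment".

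**The concern.** A site that works from the visit table and a site that works from the numbered text will retest different patients at day 30, with different tests. After day 30, the only rule that names repeat blood tests is written as if every abnormality were a raised value. Yet the laboratory values listed as haematologic dose-limiting toxicities in 3.1.1.1 are low counts, and 7.3.1 lists anaemia, decreased platelets and hypoalbuminaemia among the common events.

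Toxicity is a secondary objective (2.1.2), and 7.9.4 gives documenting reversibility as the purpose of the repeat scan. If the passage in use decides who is retested, whether an event is shown to have resolved depends partly on which page the site followed. It is also a monitoring matter for the individual patient.

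**Working it through.** The plan has no figure to reproduce here. The check sets the passages side by side.

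**1. Day-30 laboratory tests.** Two yes/no conditions give four situations.

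| Clinically significant laboratory event at off-study | AST, ALT or bilirubin above ULN or baseline at last dose | 7.9.4 | 7.9.7 table |
|---|---|---|---|
| No | No | None | None |
| No | Yes | None | Liver tests |
| Yes | No | Blood count and biochemistry | None |
| Yes | Yes | Blood count and biochemistry | Liver tests only |

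Text and table disagree on whether to test in 2 of 4 situations, and on what to test in the fourth row. A patient with a significant low platelet count and normal liver tests is retested under the text but not the table. A patient with a raised ALT that is not judged clinically significant is retested under the table but not the text. The reference time also differs: off-study assessment in one, last dose in the other.

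**2. Day-30 LVEF.**

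| State | 7.9.2.2 | 7.9.4 | 7.9.7 footnote |
|---|---|---|---|
| No drop >10% | No | No | No |
| Drop >10%, recovered by discontinuation | Optional | Not called for | Required |
| Drop >10%, still present | Optional | Should | Required |

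7.9.4 and the table disagree on who is scanned in 1 of 3 states, the recovered drop. The optional wording of 7.9.2.2 differs from the table in both drop states. At the off-study visit, 7.9.3 and the table agree.

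**3. Stop rule, low values.** Testing continues while value > ULN or value > baseline. Section 4.1 requires neutrophils of at least 1.5 and platelets of at least 100 (x 10⁹/L) at entry. Taking the entry value as baseline, a neutrophil count under 1.0 or a platelet count under 50 (the limits in 3.1.1.1) is below baseline and below ULN. Both comparisons are false, so the rule as worded calls for no repeat. The same holds for haemoglobin or albumin that has fallen below baseline. With assumed values for albumin of ULN 50, baseline 40 and current 22, neither 22 > 50 nor 22 > 40 is true.

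**4. Stop rule, raised baseline.** Two readings are possible, with B the patient's baseline:
- Literal *or*: continue while value > ULN or value > B. Testing ends at or below the lower of ULN and B.
- Higher of the two: continue while value > max(ULN, B). Testing ends at or below the higher of ULN and B.

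Section 4.1 admits ALT and AST up to 2.5 x ULN, and bilirubin with no upper limit on atazanavir. The baselines below are illustrative, in multiples of ULN:

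| Baseline | Literal *or* ends at or below | Higher of the two ends at or below |
|---|---|---|
| ALT 2.0 | 1.0 | 2.0 |
| Bilirubin 3.0 | 1.0 | 3.0 |
| ALT 0.5 | 0.5 | 1.0 |

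On the literal reading, return to a baseline of 2.0 or 3.0 does not end testing, and an ALT of 0.9 in the third patient, although below ULN, keeps it going. The 10.1 wording, return to baseline, would end testing at 2.0, 3.0 and 0.5.

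**The case against.** The best defence is that other provisions fill most of the gap. The second 7.9.5 bullet follows every unresolved adverse event in either direction, and 10.1 provides an additional haematology and biochemistry form and a post-treatment adverse event form. So a reader might infer that low-value events are not followed at all, and the documents do not support that. What stands is that the bullet names no blood test and that its end point differs from those in the neighbouring bullet and in 10.1. The cover is partial.

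A reader might also infer that laboratory follow-up can never end when baseline is above ULN. It can: it ends once the value is at or below ULN. In addition, 9.1.1 says that a pre-existing abnormality is not an adverse event unless it worsens by at least one CTCAE grade, so a stable raised bilirubin does not enter the loop. What stands is the patient who worsened and then returned to a raised baseline.

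The 10.1 entry that links additional heart scans to symptoms might be read as excluding asymptomatic LVEF drops. It describes an ad hoc form; the Off Study and 30-Day forms have their own place for the scan.

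Finally, reversibility is not a listed outcome measure, 13.2.2 plans toxicity per cycle and dose intensity, and adverse event reporting ends 30 days after the last dose (9.1.3). This limits the consequence but does not remove the contradictions.

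**Conclusion.** The inconsistency is real and can be read directly from the current text. Text and table select different patients for day-30 blood tests and for the day-30 LVEF scan, and the laboratory stop rule fails for low values and is ambiguous for raised baselines.

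The number of patients affected cannot be taken from the documents. It is tempting to derive counts from the LVEF change in 1.3 or the incidences in 7.3.1. Section 1.3 gives a mean and range but no standard deviation, and says nothing about drops that recovered by discontinuation. The 7.3.1 incidences are for all grades, not for clinically significant events that persist to day 30, and they include low magnesium, which the listed test panels do not name.

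The effect is confined to secondary safety description and patient monitoring. The response endpoint, the two-stage decision rule and the sample size are unaffected. The conclusion assumes that the empty day-30 table cells are as the sponsor set them; the same rows are filled at the off-study visit, which supports this.

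**What to change.** Reconcile 7.9.2.2, 7.9.4, 7.9.5, the 7.9.7 table with its footnotes, and the form table in 10.1, so that each test has one trigger, one scope and one stop condition, stated the same way everywhere. In particular:

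- Make the day-30 laboratory text and table agree on who is tested, on which tests, and on the reference time.
- Use one level of obligation for the LVEF repeat, and state in every place whether persistence at discontinuation is a condition.
- Word the laboratory stop condition so that it works for abnormalities in either direction and for baselines outside the normal range, and align it with the adverse event bullet and with 10.1.

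Which clinical rule applies is for the sponsor to decide; this point asks only that the passages agree. The cost is amendment wording and some table cells, and possibly a few blood tests or scans that one of the existing passages already calls for.
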